H1: Older adults randomized to volunteering (vs. control) will report lower loneliness (H1a; UCLA Loneliness Scale)²⁷ and greater quality of life (H1b; WHOQOL Scale)²⁸ at 3, 6, 9, and 12 months.

Aim 2: *To examine increased social engagement, perceived usefulness, and perceived social support as mechanisms for reducing loneliness.*

H2: Older adults randomized to volunteering (vs. control) will report greater social engagement (H2a), perceived usefulness (H2b), and perceived social support (H2c) at 6 months, which will account for the effects on reduced loneliness at 12 months.

Aim 3: *To examine conditions under which volunteering is most effective at reducing loneliness.*

H3: The effect of volunteering vs. control on loneliness will increase with greater quantity (H3a; hours per month) and satisfaction (H3b).

H4 (exploratory): Given that functional impairment impacts all proposed mechanisms, the effect of volunteering vs. control on loneliness will be strongest for those with less functional impairment at baseline.

IMPACT: *National infrastructure for volunteering programs for older adults—The Senior Corps—ensures that volunteering is **highly scalable**. Dissemination and scaling up efforts will involve connecting primary care patients and aging services clients who are lonely with The Senior Corps, which we have shown to be feasible in our companion study, The Senior Connection. Existing infrastructure will make it possible to engage a large proportion of lonely older adults in volunteering, thereby reducing loneliness, improving well-being, and promoting health.*

II. CHARACTERISTICS OF THE RESEARCH POPULATION

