Behavioral Activation Scale for Depression (BADS)—social subscale ⁴⁵	Social activation.	Kanter and colleagues present evidence of the scale's psychometric properties, including solid factor structure, internal consistency, and test-retest reliability.	2-4 minutes in-person interviews
Volunteer Functions Inventory ⁴⁶	Reasons individuals participate in volunteer activities	Konrath and colleagues demonstrated good psychometrics	3-5 minutes Volunteer condition only

		and a latent structure consistent with several subscales.	6 months and final interview
PROMIS Social Functioning Computerized Adaptive Tests ⁴⁷	Emotional support, informational support, instrumental support, satisfaction with social roles and activities, social isolation, companionship	These computerized adaptive tests measure several domains of social functioning.	5 – 7 minutes In-person interviews
Rosenberg Mattering to Others Scale ⁴⁸	Mattering to others (5 items)	This is the most commonly used measure of perceptions of mattering and has numerous reports of solid psychometrics	2 – 3 minutes In-person interviews

Quality of Life measures

Measure Name and Citation	Construct Measured	Description & Psychometric Data	Estimated Administration Time
WHOQOL-BREF ²⁸	Health-related quality of life	This brief 36 item measure assesses several domains of health related functioning and quality of life. It has excellent psychometric properties and can be used cross culturally.	10 - 15 minutes baseline and final interview
PROMIS Quality of Life scales ⁴⁹	General life satisfaction, Meaning and Purpose, Positive Affect	These measure several domains of quality of life. The purpose in life items have been empirically linked to volunteering in older adults. ⁵⁰	4 - 6 mins in-person interviews
Reminiscence Functions Scale ⁵¹	Measures reasons individuals engage in reminiscence, which is a key component of the life review intervention.	Robitaille et al. provide support for the 8 subscales and data that demonstrate adequate psychometric properties in a sample of older adults.	6 – 8 minutes Life review only 6 month and final interviews
Brief Measure of Generativity and Ego Integrity ⁵²	Generativity (perceptions of giving back, especially to younger generations) and ego integrity (looking back on one's life with meaning)	Vuksanovic and colleagues ⁵² provide data indicating that this shortened measure provides adequate construct coverage.	2 – 4 minutes In-person interviews

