
g) Analytic Procedures:

Power analysis is conducted to test treatment effects by the intent-to-treat (ITT) analysis for the primary hypothesis. We assume a conservative 20% attrition rate and a 0.3 within-subject correlation. A sample size of N = 300 (or N = 150 per treatment group) will allow us to detect a small effect size of 0.2 for loneliness, with 80% power based on a two-sided type I alpha = 0.05. The assumed within-subject correlation of 0.3 reflects the relatively long time lag between consecutive assessments. The proposed sample size also has 80% power to detect 32% mediation effects for loneliness, a continuous outcome. If full mediation is not achieved for any of the mediators considered, 32% mediation effects are sufficiently large to be of clinical importance for the outcomes of interest.

Descriptive statistics will be computed to summarize distributions of each outcome, with means and standard deviations for continuous outcomes and percent for categorical outcomes. Two-sample t tests (or the Mann-Whitney-Wilcoxon rank sum test) and Chi-squares will be used to examine balance of treatment randomization for continuous (if distributions are highlight skewed) and categorical variables. The primary hypotheses are concerned about the effectiveness of volunteering on reducing loneliness vs. control. Examination of mechanisms (mediation, Aim 2) as well as dose-response relationships (Aim 3) and moderators (Aim 3) of the intervention will also be examined. Aim 1 (and Aim 3 H4 on moderation) will be tested using longitudinal regression models, while the mediation hypothesis (Aim 2) will be examined by structural equation models, and dose-response relationships (Aim 3) by structural mean models.

The two most popular longitudinal models are the generalized linear mixed-effect models (GLMM) and the weighted generalized estimating equations (WGEE). Weighting is based on inverse probability of drop-out, extending standard GEE from valid inference only under missing completely at random to missing at random, similar to GLMMs. For inference about treatment effects, both models can be applied. However, parametric

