
Aim 1 compares subjects randomized to either the volunteering or control on loneliness (continuous variable). **H1a:** There will be a condition effect on loneliness at all time points indicating differing levels of loneliness in the direction: control > volunteering. Longitudinal models will be employed with loneliness as the response, and condition, time and their interaction as the predictors, controlling for age, gender. If a significant difference exists (a significant time by condition interaction), appropriate linear contrasts will confirm the hypothesized directional effects. For **H1b**, the same analytic strategy will be used, but with quality of life (continuous) as the response variable. Aim 2 involves mediation analysis: is to examine perceived usefulness and social support as mediators of the intervention effect on loneliness. **H2a:** Increases in social engagement at 6 months is hypothesized to mediate the effect of intervention condition on decreased loneliness at 12 months. The SEM-based mediation models will be applied, with social engagement as the mediator, intervention condition as the predictor and loneliness as the outcome, controlling for age, gender. If the null of full mediation is rejected, we will estimate direct, indirect and total effects to assess the strength of mediation. The same analytic strategy

will be used for perceived usefulness and social support (**H2bc**). **Aim 3** involves when volunteering will provide maximal benefit. **H3:** Greater hours (compliance) and satisfaction will be associated with better outcomes. We will apply the SFRM-based SMM to analyze dose-response relationships. We will first model dose using non-parametric methods and then characterize the patterns using parametric methods. This allows us to capture detailed dose and response relationships and provide more interpretable findings. **H4:** The longitudinal model for H1a will be used with functional status as a moderator variable.

h) Data and Safety Monitoring Plan:

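### Aim 1 is decided by a time-by-condition interaction without adjusting for baseline loneliness, so the sustained effect in H1a would usually be missed, and H1b names visits at which its outcome is not collected

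*Combined protocol and SAP*

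**What the plan says.** Section I (Specific Aims & Hypotheses) predicts under H1 that volunteers will report lower UCLA loneliness and "greater quality of life (H1b; WHOQOL Scale)²⁸ at 3, 6, 9, and 12 months".

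Section III.g (Analytic Procedures) restates H1a as a main effect: "There will be a condition effect on loneliness at all time points". The longitudinal model has "condition, time and their interaction as the predictors, controlling for age, gender". The decision rule follows: "If a significant difference exists (a significant time by condition interaction), appropriate linear contrasts will confirm the hypothesized directional effects." H1b is to be analysed in the same way, with quality of life as the response. The section does not say whether baseline is one of the response visits, or whether time is categorical or linear. It states no test of a condition main effect or of an average effect.

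The power statement in the same section says that 300 participants "will allow us to detect a small effect size of 0.2 for loneliness", "with 80% power based on a two-sided type I alpha = 0.05", assuming 20% attrition and a within-subject correlation of 0.3.

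Section III.e schedules the UCLA Loneliness Scale at every time point. The WHOQOL-BREF entry reads "10 - 15 minutes baseline and final interview". The 2022 addendum adjusts the MOCA and adds two measures, and leaves the WHOQOL-BREF schedule as it was.

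**The concern.** The hypothesis and its test ask different questions. H1a is about whether a difference exists at each follow-up visit. The interaction is about whether the difference varies over time, and the contrasts that would address H1a are conditional on it. A benefit that appears by month 3 and holds to month 12, which would be a good result for this intervention, is the pattern such a test handles badly.

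Loneliness is the primary outcome, so a true effect of the planned size would usually leave the trial with no planned route to claim it. Presenting the contrasts after a non-significant interaction would depart from the plan on its main result.

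Two further points concern the same model. Baseline loneliness is measured on everyone but is not a covariate, which gives up precision at no saving. And H1b commits the trial to three visits of WHOQOL results for which no data will exist.

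**Working it through.** **Inputs (section III.g unless noted).** Standardised effect 0.2 with SD 1; correlation ρ = 0.3; 150 per arm, or 120 completers after 20% attrition; two-sided 0.05; visits at baseline, 3, 6, 9 and 12 months (section III.a). Assumptions added here: compound symmetry and equal attrition by arm. Dropout is taken as none, 20% lost immediately after baseline, or 5% lost at each follow-up visit (gradual).

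**The plan's 80%.** For an average over the four follow-up visits, the variance factor per arm is (1 + 3ρ)/4 = 0.475. With baseline as a covariate it is 0.475 − ρ² = 0.385. Power is approximately Φ(0.2/√(2v/n) − 1.96).

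- Unadjusted, n = 120: 0.2/√(0.95/120) = 2.248, power 61.3%. With n = 150, 71.0%.
- Adjusted, n = 120: 0.2/√(0.77/120) = 2.497, power 70.4%. With n = 150, 79.7%.
- With gradual dropout: 66.5% unadjusted, 75.2% adjusted.

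None of the two-sided calculations tried that include the 20% attrition reaches 80%. The adjusted average comes close (79.7%) only if attrition is ignored. The plan gives no formula, so this is a failure to reproduce the figure and does not identify a specific error.

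**Interaction, follow-up visits only.** A constant effect gives a noncentrality of 0 on 3 df, so the rejection rate is alpha, 5% (simulation 5.1–5.3%).

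**Interaction, baseline included, categorical time (4 df).** The differences are (0, 0.2, 0.2, 0.2, 0.2), with mean 0.16. The sum of squared deviations is 0.0256 + 4 × 0.0016 = 0.032. The noncentrality is (n/2) × 0.032/(1 − 0.3) = 0.02286n.

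- n = 120: 2.74, power 22.5% (simulation 22.4%).
- n = 150: 3.43, power 27.6% (simulation 27.0%).
- Gradual dropout: 26.4%. All 20% lost immediately after baseline, with their baseline values retained: 25.1%.

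Reaching 80% needs a noncentrality of 11.94, which is 11.94/0.02286 ≈ 523 completers per arm, or 523/0.8 ≈ 654 randomised per arm. Alternatively it needs a true effect of 0.37 (n = 150) to 0.42 (n = 120).

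**Interaction, baseline included, linear time (1 df).** Centred times are −6, −3, 0, 3, 6, with sum of squares 90. The slope difference is 0.2 × (−3 + 0 + 3 + 6)/90 = 0.01333. Its standard error at n = 120 is √(1.4/(120 × 90)) = 0.01139, so z = 1.17 and power is 21.6%. At n = 150 it is 25.8%.

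**Effect growing linearly from 0 at baseline to 0.2 at month 12.** The 4-df test has 18.2–22.0% and the slope test 31.0–37.3% (n = 120 to 150). The adjusted average has 34.5–41.5%.

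**Other correlations, constant effect, n = 120 to 150.**

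| ρ | 4-df interaction | Baseline-adjusted average |
|---|---|---|
| 0.1 | 18.1–21.9% | 78.8–87.0% |
| 0.3 | 22.5–27.6% | 70.4–79.7% |
| 0.5 | 30.8–38.1% | 71.6–80.7% |
| 0.7 | 49.9–60.5% | 82.7–90.1% |

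**Single-visit variance at ρ = 0.3.** Change from baseline: 2(1 − 0.3) = 1.40. Raw score: 1.00. Baseline-adjusted score: 1 − 0.09 = 0.91.

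**H1b.** Visits promised: 3, 6, 9, 12 months. Follow-up visits with WHOQOL-BREF data: 12 months only. With two measurements the interaction is a 1-df comparison of change. Taking 0.2 and 0.3 as illustrative for WHOQOL-BREF and n = 120, it has 25.8% power, against 36.8% for the baseline-adjusted 12-month score.

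**The case against.** The strongest reply is that baseline belongs among the response visits. Section III.a lists it among the repeated assessments, and an interaction is a familiar way to show that two arms diverge after a common start. On that reading the 5% figure does not apply, and baseline is used, though inefficiently, through change from baseline. This is the more natural reading, so the fair headline is 22–28% rather than 5%. It is still far too low.

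H1 does not say that the effect is equal at every visit. That is correct, and with a linearly growing effect the slope test comes close to the adjusted average. But the plan does not specify a slope, and every form of the gate still misses that pattern more often than not.

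The correlation could exceed 0.3. At 0.7 the 4-df test reaches 50–61%, so the statement that the effect is mostly missed depends on the plan's own value. The adjusted average has higher power at every correlation tried.

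The plan never says that a non-significant interaction makes Aim 1 negative. That is also true, but it offers no other rule.

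Two limits of the remedy stand. A significant average does not show an effect at every visit, and 70–75% remains below the stated 80%. Finally, omitting the baseline covariate loses efficiency (about 9 points) without invalidating the test, and for H1b the two-visit interaction is a valid test. The H1b fault is the visit schedule. PROMIS quality-of-life scales are taken at in-person interviews, but H1b does not name them.

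**Conclusion.** The concern holds. As written, the primary hypothesis is decided by a test of a different question. For a constant 0.2 effect at correlation 0.3, that test fails roughly 72–78% of the time with baseline as a response visit, and 95% of the time with follow-up visits alone. A baseline-adjusted average effect would have 70–75% power after the planned attrition. Most of the loss comes from the interaction rule; the missing baseline covariate accounts for about 9 points of power on the average-effect test. These figures rest on compound symmetry and equal attrition by arm. The H1b conflict needs no assumptions: three of its four stated visits have no WHOQOL-BREF data.

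**What to change.** In section III.g:

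- Make the primary H1a test the 1-df condition effect averaged over 3, 6, 9 and 12 months. Take it from a model with the four follow-up scores as responses, categorical time, condition, their interaction, and baseline UCLA loneliness, age and gender as covariates. A model with baseline as a response and a common baseline mean in both arms is an equivalent alternative. State the same specification for the GLMM and the WGEE.
- Report the four visit-specific differences with confidence intervals whatever the interaction p-value, and say that they describe the pattern and are not separate confirmatory claims. Keep the interaction as a secondary test of whether the effect changes over time.
- If a claim at every visit is truly intended, state that rule and its power instead.
- Restate the power for the test chosen, since 80% is not recovered with the plan's own attrition.

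In section I and section III.g, restate H1b as a 12-month comparison of WHOQOL-BREF adjusted for its baseline value.

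The cost is revised analysis wording and a narrower H1b. No participants, visits or measurements are added.

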The ITT analysis for Aim 1 provides intervention effects averaged over all subjects randomized to the intervention conditions. When intervention compliance (volunteering hours/satisfaction for subjects in the volunteering condition) demonstrates a dose-response relationship, as we hypothesize in Aim 3, complier average causal effects (CACE) are appropriate; thus we will use them to test Hypothesis 3. CACE is a compliment to ITT analyses and provides an answer to a different question than is answered by ITT analyses (i.e., the result of complying vs. being offered an intervention).⁷¹ CACE provides valid causal inference because it maintains randomization and includes all subjects in the analysis, as with ITT.⁷² CACE provides different intervention effects for individuals depending on their levels of compliance, which can be quite informative, especially when there is large variability in intervention compliance and strong dose-response relationships. The ITT and CACE estimates from a similar intervention study by Gruenewald, et al.⁷³ show that not only were the CACE effect sizes much larger than their ITT counterparts (small ITT vs. large CACE effect size), but the temporal trend also reversed; while the ITT effect sizes decreased, the CACE effect sizes increased from 4 months to 12 months post intervention, indicating substantial heterogeneity in intervention compliance and strong dose-response relationships. Since volunteering time is only required for the volunteering condition, standard statistical models cannot be used to perform CACE analysis. The CACE approach enables an estimate of the treatment effect at each level of "compliance" (i.e., amount of hours volunteered), without the need for a measure of compliance in the control group. In this way, we will be able to tell how well volunteering reduces loneliness at different "doses" of volunteering. The two most popular methods for addressing intervention compliance are the parametric principal stratification (PS) and the semi-parametric structural mean model (SMM).⁷⁴⁻⁷⁶ Unlike the PS, the SMM not only allows for continuous dose variables, but also requires no parametric model for data distribution such as normality, thereby yielding robust inference for a broader class of data distributions. We will use the latest SMM based on the structural functional response models (SFRM) for our CACE analysis, which not only allow for continuous, but also multiple dose variables.⁷⁴⁻⁷⁶ We are particularly interested in potential non-linear dose-response relationships so that we may determine optimal dose intervention whereby increased exposure (i.e., number of hours volunteered) becomes less worthwhile (in terms of reducing loneliness).

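### H1a predicts an effect at every visit, but no decision rule, contrast list, significance level or multiplicity adjustment says how the contrasts after the interaction test confirm it

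*Combined protocol and SAP*

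**What the plan says.** The Specific Aims state H1 for months 3, 6, 9 and 12. Section III.g (Analytic Procedures), Aim 1, restates H1a as: "There will be a condition effect on loneliness at all time points indicating differing levels of loneliness", with control higher than volunteering. The model has condition, time and their interaction, controlling for age and gender. If the interaction is significant, then "appropriate linear contrasts will confirm the hypothesized directional effects".

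The power paragraph of the same section says the sample "will allow us to detect a small effect size of 0.2 for loneliness", "with 80% power based on a two-sided type I alpha = 0.05". It does not tie that effect to a visit or to an average over visits. Its other inputs are stated as "We assume a conservative 20% attrition rate and a 0.3 within-subject correlation".

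No primary visit is named for H1a; month 12 is singled out only for mediation (H2). The 2022 addendum does not change the analysis.

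**The concern.** The every-visit wording is a hypothesis, not a rule for deciding it. Two readings of the contrast step are open, and each has a problem.

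- **All four visits must be significant.** This is strict on false positives, but it may leave the trial little chance of success at the effect it was planned for.
- **Visits may be claimed one by one.** The interaction test then acts as a gate. It limits errors when there is no effect anywhere, but a real effect at one visit helps to open it, and the remaining null visits are tested without adjustment.

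An effect that changes over time is not remote. The section's discussion of complier effects cites a similar trial in which "while the ITT effect sizes decreased, the CACE effect sizes increased from 4 months to 12 months post intervention". What is at stake is whether the primary hypothesis is called met, and which visits are reported as showing benefit.

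**Working it through.** **Inputs from section III.g:** 150 per arm, or 150 × 0.8 = 120 after 20% attrition; within-subject correlation 0.3; effect 0.2 SD; two-sided 0.05; four follow-up visits.

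**Assumptions:** equal correlation between all visits; 0.05 for the gate and for each contrast (the Aim 1 paragraph gives no level); a Wald interaction test on 4 df if baseline is a time level, 3 df if not; normal approximation.

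**1. The plan's 80%.** The mean of four visits has variance factor (1 + 3 × 0.3)/4 = 0.475. Power = Φ(0.2·√(n/2)/√0.475 − 1.96).

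- n = 120: Φ(1.549/0.689 − 1.96) = 61%.
- n = 150: Φ(1.732/0.689 − 1.96) = 71%.
- Adjusted for baseline, the factor is 0.475 − 0.3² = 0.385. Power is 70.4% at 120 per arm and 79.7% at 150.

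The 80% is not reproduced from all the stated inputs together. The nearest two-sided match is a baseline-adjusted average over visits with no attrition, not a rule requiring every visit.

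**2. All four visits required, constant 0.2 SD.** Each visit's Z has mean 0.2·√(n/2), which is 1.549 or 1.732, so one visit is significant 34% or 41% of the time. By simulation at correlation 0.3, all four are significant 5.3% (n = 120) or 8.5% (n = 150) of the time. The gate alone passes 22-28% of the time with baseline as a time level. Without baseline it passes 5% of the time, because a constant effect then produces no interaction. Gate and all four visits together: under 3%.

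**3. Visits claimed singly, real effect at one visit only.** Simulated chance that the gate passes and at least one null visit is falsely claimed. Contrasts are differences at the visit; ranges cover 120-150 per arm and both forms of the gate.

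| True effect at the one visit | False claim, either direction | False claim favouring volunteering | Either direction, Holm behind the gate |
|---|---|---|---|
| 0.2 SD | 5.8-6.8% | 2.0-2.5% | 2.1-2.3% |
| 0.3 SD | 9.0-10.0% | 3.4-4.2% | 3.0-3.3% |
| 0.4 SD | 11.5-12.5% | 5.0-5.8% | 3.8-4.2% |
| 0.5 SD | 12.9-13.4% | 6.2-6.6% | 4.4-4.7% |

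With no effect at any visit, the gated rate in either direction is 3.3-3.7%. Once the gate always passes, the limit for three null visits is 13.6%. If the contrasts are changes from baseline, the either-direction figures are 5.0-7.8% at 0.2 SD and 11.9-12.5% at 0.5 SD.

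**4. The averaged contrast when only one visit has an effect e.** The averaged effect is e/4, so power for benefit is Φ((e/4)·√(n/2)/√0.475 − 1.96). With 130 per arm, a value assumed between 120 and 150: e = 0.2 gives Φ(0.585 − 1.96) = 8%; e = 0.5 gives Φ(1.462 − 1.96) = 31%.

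**The case against.** The strongest reply is that the text does point to all four visits. Under that rule the H1a decision has no inflation and needs no adjustment, and the interaction gate also keeps the error below 5% when nothing works. That is correct. It turns the problem into one of power, because the plan never adopts the rule and its 80% does not describe it.

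Three stronger readings are tempting, and the documents do not support them.

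- **A reader might infer that the trial falsely claims benefit about 13% of the time.** That figure is close to a ceiling. It needs about 0.5 SD at exactly one visit and nothing at the other three, and about half of it is false harm. At the plan's 0.2 SD the total is about 6%, and false benefit about 2%. The cited trial's effects are described as small and decreasing, which does not establish a fall from 0.5 SD to zero.
- **A reader might infer that an any-visit rule would succeed most of the time.** Without the gate it does, at 71-78% for a constant 0.2 SD. The plan has the gate; with it the figure is 20-25% if baseline is a time level and about 5% if not.
- **A reader might infer that four separate contrasts at 0.05 are planned.** The text would also permit an averaged or trend contrast. The 0.05 per visit is an assumption here.

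It is also fair to say that deciding H1a on an average changes the primary comparison and removes the gate. Naming month 12, or requiring all four visits, would also end the ambiguity.

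**Conclusion.** The concern holds in limited form: section III.g predicts an effect at every visit but does not turn this into a decision rule, and the confirming contrasts have no list, level or adjustment. Read strictly, H1a would be met about 5-8% of the time before the gate, and under 3% after it, at a constant 0.2 SD. Read visit by visit, null visits are protected only when every visit is null; the false-claim rate then runs from about 6% to about 13% as a one-visit effect grows from 0.2 to 0.5 SD.

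The absence of a rule is plain from the text. The sizes rest on equal correlation of 0.3, 120-150 per arm and the assumed 0.05 levels. This is not evidence that the H1a decision itself carries a 13% error rate.

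**What to change.** In the Aim 1 paragraph of section III.g, replace the interaction-then-contrasts sentence:

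1. H1a is decided by one prespecified contrast from the same model, the condition difference averaged over months 3 to 12, at two-sided 0.05, in place of the interaction gate.
2. If it is significant, report the four visit contrasts with Holm-adjusted p-values, and claim a visit only if its adjusted p-value is below 0.05.
3. Keep the every-visit wording as a description of the expected pattern, not as the success criterion.

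For a constant 0.2 SD effect the averaged contrast has about 61-71% power, against 22-28% or 5% for the gate alone. In the one-visit scenarios this sequence brings false visit claims to about 2%. If the sponsor prefers to keep the interaction gate, Holm across the four visits still holds them to roughly 2-4.7%, but the low power of the gate remains.

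The cost is a text change, with the same fitted model and no new data. It does change what decides the primary hypothesis, so it should be dated and made before unblinded results are seen. Individual visit claims lose some power, and the averaged contrast is weak if the effect is confined to one visit (about 8-31%, step 4).

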Credibility and Expectancy Questionnaire (CEQ)	Subject's expected benefits	Questionnaire to assess subject's expected benefits of the program	2 minutes Baseline and 12 month interview

Sexual Orientation Concealment Scale (SOCS)	Subject's concealment of sexual identity	Questions designed to assess lesbian, gay, and bisexual (LGB) individual's active concealment of their sexual minority status	2 minutes Baseline for those who answered as LGB on demographic form. 6 and 12 months – for those in volunteer group who had answered as LGB on demographic form at baseline.
Randomization Feedback	Subject's experience with randomization	Feedback from the subject on the randomization process and their satisfaction with the group to which they were randomized	5 minutes 12 month interview

Social connectedness measures

Measure Name and Citation	Construct Measured	Description & Psychometric Data	Estimated Administration Time
Revised UCLA Loneliness Scale, version 3 ²⁷	Global loneliness	Yields a continuous score, with greater scores indicating greater loneliness; it will be used to assess loneliness at all assessment time points. It has demonstrated excellent internal consistency, test re-test reliability, and construct validity (associations with social support and social network size), ²⁷ including with older adult samples. ^{13,27} Importantly, it has been shown to be sensitive to change as a result of intervention. ⁴⁰	3 - 5 mins all time points
De Jong Gierveld Loneliness Scale ⁴¹	Social and emotional loneliness	It had demonstrated excellent psychometric properties and construct validity.	3 - 5 mins all time points
Lubben Social Network Scale ⁴²	Social network size and frequency of contact.	This set of self-report questions has been shown to predict premature mortality.	3 – 5 mins; all time points
Interpersonal Needs Questionnaire (INQ) ^{43,44}	Thwarted belongingness (TB), perceived burdensomeness (PB).	[name] et al. ⁴³ report high internal consistency coefficients for the thwarted belongingness ($\alpha=.85$) and perceived burdensomeness subscales ($\alpha=.89$). In support of construct validity, both subscales were found to positively correlate with suicidal ideation.	3 – 5 minutes all time points

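### The Aim 2 mediation model leaves out loneliness before month 12, so a mediator that only follows reduced loneliness can be reported as its mechanism

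*Combined protocol and SAP*

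**What the plan says.** Section I (Specific Aims) predicts in H1 that the volunteering arm will be less lonely "at 3, 6, 9, and 12 months". Section III.g repeats this for H1a: "There will be a condition effect on loneliness at all time points".

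H2 in Section I places the three mediators "at 6 months, which will account for the effects on reduced loneliness at 12 months". Section III.g gives the same timing for the first mediator: "Increases in social engagement at 6 months is hypothesized to mediate the effect of intervention condition on decreased loneliness at 12 months". It describes the SEM as one "with social engagement as the mediator, intervention condition as the predictor and loneliness as the outcome, controlling for age, gender", and the same strategy "will be used for perceived usefulness and social support". The decision rule is: "If the null of full mediation is rejected, we will estimate direct, indirect and total effects to assess the strength of mediation".

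No loneliness score from baseline, month 3 or month 6 is listed in this model, nor is a baseline mediator value. The scores exist. The measures table in Section III.e says of the UCLA scale that "it will be used to assess loneliness at all assessment time points". Most of the social scales are given at the in-person interviews, so they are repeated at months 6 and 12, and some are given at every visit. The 2022 Addendum moves visits to phone, video or online but keeps these time points.

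Neither the protocol nor the Addendum plans a cross-lagged model, a reverse-direction model or a sensitivity analysis for the mediator-outcome path. The distribution-free SEM in Section III.g deals with distributional assumptions and missing data, not with direction.

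**The concern.** Randomisation protects the comparison of arms on the mediator and on loneliness. It does not protect the path from mediator to loneliness. Placing the mediator six months before the outcome would help establish order if the outcome had not yet moved, but the plan's own hypothesis is that it moves by month 3.

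Suppose volunteering lowers loneliness by some other route. Less lonely people then report more engagement, usefulness and support at month 6, and loneliness persists to month 12. The 6-month mediator predicts 12-month loneliness without having any effect on it. Aim 2 exists to identify mechanisms, so the risk is a mechanism claim that runs the wrong way, with three mediators each offering a chance of it.

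**Working it through.** **The plan's own mediation figure.** Section III.g claims 80% power for a 32% mediated share. It gives no path coefficients, no total effect for that calculation and no named test, so the figure cannot be reproduced exactly. With a total effect of 0.2 SD, a joint-significance test and the most favourable split of the two paths, power is at most 77% (N = 300) or 64% (N = 240). Nothing below depends on this; 32% serves only as the plan's yardstick for an important share.

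**Inputs from Section III.g.** N = 300 and 20% attrition give 300 × 0.8 = 240 completers. The effect is d = 0.2 SD, the within-subject correlation ρ = 0.3, and alpha 0.05 two-sided.

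**Assumptions.** The same-visit mediator-loneliness correlation is r = 0.4 or 0.6. An alternative ρ of 0.6 is also shown. Variances are 1 within arm, and mediation is declared when both paths are significant.

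**Scenario with true mediation zero.** The 6-month mediator is −r × (6-month loneliness) plus noise. Loneliness at month 12 depends on 6-month loneliness with coefficient ρ and on condition, so that the total effect stays at d. The planned model then sees, in absolute value:

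- condition to mediator: a = r·d, with SE √(4/240) = 0.129
- mediator to outcome: b = r·ρ, with SE √((1 − r²ρ²)/240)
- apparent mediated share: ab/d = ρ·r²

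The approximate false-mediation rate is the product of the two rejection probabilities.

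| ρ | r | Apparent share | a (z; P reject) | b (z; P reject) | Product | Simulations |
|---|---|---|---|---|---|---|
| 0.3 | 0.4 | 4.8% | 0.08 (0.62; 9.5%) | 0.12 (1.87; 46.5%) | 4.4% | 4.3%, 6% |
| 0.3 | 0.6 | 10.8% | 0.12 (0.93; 15.3%) | 0.18 (2.83; 81%) | 12.4% | 11.5–13% |
| 0.6 | 0.4 | 9.6% | 0.08 (0.62; 9.5%) | 0.24 (3.83; 97%) | 9.2% | 8–9% |
| 0.6 | 0.6 | 21.6% | 0.12 (0.93; 15.3%) | 0.36 (5.98; ~100%) | 15.3% | 15–17% |

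The joint rate is limited mainly by the weak condition-to-mediator path, not by any protection on the mediator-to-outcome path. That second path alone is falsely significant in 28–93% of simulated trials for r from 0.3 to 0.7 at ρ = 0.3, against 4–5% once 6-month loneliness is in the model. A larger treatment effect raises the joint rate: at 0.3 SD and r = 0.6 it is 24% (ρ = 0.3) or 28% (ρ = 0.6).

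**The plan's own rule.** Under the same scenario with ρ = 0.3, full mediation goes unrejected in 67–72% of trials. Most of this is low power. A single-visit effect of 0.2 SD with 120 per arm has z = 0.2/0.129 = 1.55 and power 34%, so 100 − 34 = 66% would go unrejected with no apparent mediation at all.

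**What adjustment does.** Adding 6-month loneliness brings the apparent share to zero and the joint rate to about 1% or less at d = 0.2. Adding only baseline or only month-3 loneliness lowers the apparent share from 15% to 11% (r = 0.7, ρ = 0.3). Baseline loneliness and baseline mediator together do not lower the false-positive rate (16% against 15% at ρ = 0.6, r = 0.6).

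**What 6-month adjustment costs.** Now let mediation be real and complete, with the mediator driving same-visit loneliness, so that a = d/r. At r = 0.4 and stability 0.3, a = 0.5 (z = 3.87; 97%) and b = 0.12 (46.5%), giving 45% detection. At stability 0.6, b = 0.24 (97%), giving 94%. If mediator and residual loneliness are equally stable with coefficient s, 12-month loneliness equals s × (6-month loneliness) plus a condition term plus noise. The mediator's coefficient given 6-month loneliness is then exactly zero, and simulated detection falls to 4–5%. If the mediator is the more stable of the two, detection is 20–66% instead of 72–96%.

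**The case against.** A reader might infer that the trial will report a reversed mechanism. The documents do not support that. They show only that the model cannot exclude it, and at the plan's own ρ and d the false-mediation rate is 4–13% for r of 0.4 to 0.6. At r = 0.3 it is about 2%. The apparent share at ρ = 0.3 stays between 3% and 15% for r from 0.3 to 0.7, well below 32%. It passes 32% only at the extreme assumed pair ρ = 0.7, r = 0.7 (34%).

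The rates above also come from a joint-significance test that the plan does not name, so they illustrate the problem and are not error rates of the stated procedure. That stands. It does not rescue the plan, because its full-mediation test contains nothing that bears on direction.

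The word for increases in H2a could mean change from baseline, which would bring in the baseline mediator. Change in the mediator up to month 6 can still follow change in loneliness over the same months.

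The strongest objection concerns the remedy. Six-month loneliness is concurrent with the mediator and may be its effect. Requiring the mediator path to survive that adjustment would replace a modest false-positive risk with a possibly large loss of true findings. This stands in full and shapes the fix.

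**Conclusion.** The point holds as a limit on what Aim 2 can show: as specified, the analysis does not separate a mediator that lowers loneliness from one that follows it. With 240 completers, d = 0.2 and true mediation zero, false mediation is about 4–6% (r = 0.4) to 12–13% (r = 0.6) at ρ = 0.3, and about 9–16% at an assumed ρ of 0.6. These figures rest on an assumed r and an assumed joint-significance test. The defect itself rests only on the stated timing and the covariate list. Aim 1 and its intention-to-treat analysis are not affected.

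**What to change.** Keep the planned SEM as the main Aim 2 analysis, and add baseline loneliness, the baseline mediator and month-3 loneliness, which precedes the mediator. Because month-3 loneliness is measured after randomisation, give it its own path from condition so that the total effect is preserved. This reduces the problem but does not remove it.

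Pre-specify two sensitivity analyses for each mediator, reported beside the main estimate:

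- (a) a model that includes 6-month loneliness, with its residual correlated with that of the 6-month mediator and a path to 12-month loneliness;
- (b) the mirror path, from 6-month loneliness to the 12-month mediator.

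Do not make (a) a condition for claiming a mechanism, since it can remove mediation already complete by month 6. If the models disagree, state that the direction is not established.

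The cost is wording in the analysis section, some extra modelling and more cautious causal language. All the scores are already scheduled.
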